We will enroll all consenting eligible clients and survey them at baseline, month 6, 12 and 18 following delivery. For those who miscarry, a final survey will take place 6 months after the miscarriage to assess successful transition to receive HIV care at the HIV clinic. At all sites, HIV+ adult patients who are early enough in their gestation period to be eligible for the study will be informed of the study and screened for potential depression by trained peer mothers using the EPDS-2. The screening will take place in a private room and those who screen positive will receive depression psycho-education. Eligible women who express interest in participating in the study will be connected by the peer mother to the study coordinator (via phone if the coordinator is not at the clinic that day) so that the coordinator can describe the study in detail, confirm eligibility and obtain written consent; these procedures are done during the same clinic visit, or the next day that the coordinator is at the clinic.

Qualitative data will be collected from peer mothers and midwife nurses at baseline, 12 and 24 months, at the intervention sites to assess: successes and challenges in screening, diagnosing and treating patients for depression; the training and supervision process; and impact of depression and its treatment on pregnancy and PMTCT care, clinic functioning, and provider job satisfaction and burnout. We will also interview 40 client participants (20 clinically depressed who were treated, and 20 not treated) at their final study assessment to assess their experiences with pregnancy.

Data analysis

Statistical Analysis. We will first compare clinic-level differences, using standard t-tests or, where the observations per clinic vary, t-tests weighted by cluster-size. Like most cluster RCTs, we do not have the 20+ clusters needed to reliably adjust standard errors for clustering, so we will use the conventional approach of using regression methods on individual level data for most analyses, but will conduct sensitivity analyses using a range of plausible ICC values for the outcomes.

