Primary Aim 1: intervention effects on primary outcomes. We will use logistic regression to test for differences between the two study arms on (i) PMTCT adherence, coded as a binary variable, at each stage of the PMTCT care continuum, and (ii) maternal viral suppression. The regression models will include patient characteristics such as age, CD4 and HIV disclosure status that may explain variance in observed differences. We will also explore significant interactions between the covariates and study arm to assess which patient types are likely to be adherent and virally suppressed in depression care vs. usual care. The effect of depression care on PMTCT adherence will be examined using intention to treat as the primary approach. We will use a repeated-measures model that will allow us to incorporate correlation in measurements of each person over time. The sample size of individuals for such models is adequate. The model formulation is: $\text{adherence}_{it} = \alpha + \beta G_i + \gamma(t) + \delta G_i \times t + \theta_i + \varepsilon_{it}$ where i is individual, t is continuous time, G is binary indicator of treatment group, β allows for baseline differences between the two groups, γ is the time trend in the outcome common to both groups, and δ is the interaction of treatment group and time, and shows the intervention effect (i.e. effect of depression care relative to usual care). Further, θ_i is an individual-level random effect (to allow for variation across participants) and ε_{it} is time period-specific error. With a vector of individual-level covariates X_i included in the model, we can assess main effects of patient characteristics and interactions between these X_i and indicator of treatment group. Such a model will allow us to test for significance of potential mediators: e.g., do effects of the depression care model vary by the patient's physical health at baseline? As the primary approach is intention-to-treat, the estimates will capture the average benefit for depressed patients, regardless of compliance or use of depression treatment. A secondary "completers only" analysis will be conducted as well. In addition, we will conduct a dose-response type analysis to explore the relationship between continuous implementation variables (e.g. treatment sessions attended), which are collected for all participants, and primary outcomes. Further, to better understand how or why the intervention exerted its effect, we will model the relationship

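### The repeated-measures model tests whether the effect varies by patient characteristic with X×G, but the plan's own intervention effect is G×t, so the moderation test needs X×G×t

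*Combined protocol and SAP*

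**What the plan says.** The passage is in the combined protocol and SAP, under Data analysis, in the paragraph on Primary Aim 1. The model contains an intercept, βG, a common time trend, δG×t, a person-level random effect and a residual. The plan defines the pieces as follows:

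- Time and arm: "t is continuous time, G is binary indicator of treatment group".
- Arm main effect: "β allows for baseline differences between the two groups".
- Arm-by-time term: "δ is the interaction of treatment group and time, and shows the intervention effect".

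It then adds a vector of covariates X, with which "we can assess main effects of patient characteristics and interactions between these X_i and indicator of treatment group". The example question for this extended model is "do effects of the depression care model vary by the patient's physical health at baseline". Neither X×t nor X×G×t is written anywhere.

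Earlier in the same paragraph, for the logistic regressions at each stage of care, the plan says "We will also explore significant interactions between the covariates and study arm". Those models contain no arm-by-time term.

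**The concern.** The question is whether the intervention effect depends on X. The plan places that effect in δ, but the interaction it offers attaches X to G, whose coefficient is β. The term named for the test is therefore not the term that would carry the answer.

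The error can run in two directions. If women with and without a characteristic already differ between arms at baseline, by an amount that persists, X×G can be significant when depression care works equally well in both groups. If a real differential effect coincides with an opposite baseline gap, X×G can hide it. At stake is the exploratory statement about which patients benefit from depression care.

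This is separate from the plan's use of the word mediators for what its example shows to be a moderation question. Correcting that word would leave the interaction term unchanged.

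**Working it through.** The documents give no power, alpha or effect size for this test, so there is no stated figure to reproduce.

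**Algebra.** Add λX + κXG to the plan's model. The depression-care minus usual-care contrast at time t is

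(β + κX) + δt.

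Its slope in t is δ for every X. With λX + κXG + μXt + ηXGt, the contrast is

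(β + κX) + (δ + ηX)t,

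and the slope is δ + ηX. Only η lets the effect, as the plan defines it, vary by X. If η is non-zero but omitted, then with balanced visits and exchangeable correlation the fitted X×G coefficient estimates κ + η·t̄, where t̄ is the mean visit time. That is the baseline gap plus a time-average of the differential effect.

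**Simulation.** From the documents: 400 women, 8 clinics of 50, 4 v 4, and four surveys ("survey them at baseline, month 6, 12 and 18 following delivery"). Assumed: times equally spaced and scaled 0 to 1, continuous outcome with SD 1, within-person correlation 0.5, X at 50%, two-sided 5%, no cluster adjustment, 2,000 runs. Gaps and clinic slope SDs are in outcome SDs.

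| Scenario | X×G alone: mean, rejection | X×G×t: mean, rejection |
|---|---|---|
| No gap, no moderation | 0.00, 5.8% | 0.00, 5.1% |
| Clinic X-slope SD 0.2, no moderation | 0.00, 13.9% | 0.01, 5.1% |
| Clinic X-slope SD 0.3, no moderation | 0.01, 23.2% | −0.01, 5.3% |
| Differential effect growing to 0.5, no gap | 0.25, 35.3% | 0.50, 75.4% |
| Same effect, baseline gap −0.25 | 0.00, 4.9% | 0.50, 74.3% |

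The last two rows match the algebra: t̄ = 0.5, so 0 + 0.5×0.5 = 0.25, and −0.25 + 0.25 = 0.

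**Hand check of the clinic-variation rows.** SE(X×G) = √[(0.5 + 0.5/4)×4/100] = 0.158. A clinic slope SD of 0.2 gives an arm-level gap with SD 0.2×√(1/4 + 1/4) = 0.141. The test statistic then has SD √[1 + (0.141/0.158)²] ≈ 1.34, and P(|Z| > 1.96/1.34) ≈ 14%. For 0.3 the same steps give about 24%.

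**On the percentage-point scale.** Assumed: adherence 70% (variance 0.21), correlation 0.4, visits at 0, 1, 1.5 and 2 years.

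- SE(X×G) = √[0.21×(0.4 + 0.6/4)×4/100] = 0.068.
- The sum of squares of time is 2.1875, so SE(X×G×t) = √[0.21×0.6/2.1875×4/100] = 0.048 per year.
- Clinic slope SDs of 5 and 10 points give X×G rejection of about 8% and 17% with no moderation.

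**Power by shape of the differential effect**, with the same standard errors. X×G is driven by the mean over the four visits, and X×G×t by the least-squares slope.

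| Differential effect at the four visits (points) | X×G | X×G×t |
|---|---|---|
| 0, 10, 15, 20 (grows) | 11.25/6.8 = 1.65, 38% | 10/4.8 = 2.08, 55% |
| 0, 20, 20, 20 (immediate, stable) | 15/6.8 = 2.21, 60% | 10.3/4.8 = 2.14, 57% |
| 0, 20, 15, 10 (wanes) | 11.25/6.8 = 1.65, 38% | 5.43/4.8 = 1.13, 20% |

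A binary-data simulation of the growing pattern (1,500 runs) gave 35.7% v 53.5%. With growth to 30 points it gave 69.7% v 88.1%.

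**The case against.** *The wording may be shorthand.* The sentence is permissive, no expanded equation is given, and the plan has just named δ as the effect, so an analyst might interact X with G×t as well. That is possible. But G is explicitly defined as the treatment-group indicator and no three-way term appears, so an analyst who follows the text fits X×G.

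*Randomization removes the gap in expectation.* This stands. With no clinic variation, chance differences among women are already in the standard error and X×G rejects at about 5%. A reader might infer that the plan will routinely report baseline gaps as benefit. Under stable gaps of 10, 15 and 20 points, X×G does reject in 32%, 60% and 87% of simulated trials, but those rates are conditional on an assumed gap for which the documents give no basis. Even with a clinic slope SD of 10 points, the gap has SD 7.1 points and exceeds 20 points in only about 0.5% of trials.

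*Patient mix is not the mechanism.* This also stands. A difference between clinics in how common X is gets absorbed by the X main effect. The relationship of X to the outcome has to differ between arms before treatment.

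*X×G does not always lose power.* Correct: the three-way term has clearly more power only when the differential effect grows over time.

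*Part of the excess reflects unadjusted clustering.* True, and the plan says it will run sensitivity analyses over a range of ICC values. Those would widen the uncertainty. They would not make X×G measure variation in δ.

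**Conclusion.** The point holds as a mis-specified exploratory test. By the plan's own definitions, X×G leaves the intervention effect constant across patients, and its coefficient combines a baseline gap with a time-averaged differential effect. This follows from the algebra and needs no numerical assumption.

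The size does rest on assumptions. With clinic-to-clinic variation in the X-outcome slope of 0.2 to 0.3 SD, false moderation appears in about 14% to 23% of trials, against about 5% for X×G×t. With smaller variation (5 points at 70% adherence) it is about 8%, and with none it is nominal. The 5% for X×G×t assumes that the clinic variation is constant over time; variation in the X-by-time slope would inflate that test too.

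The documents do not support reading this as a flaw in the main result. The primary arm comparison is untouched, and in the per-stage logistic models covariate-by-arm is the right moderation term.

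**What to change.** Write out the extended repeated-measures model with X, X×G, X×t and X×G×t. State that X×G is the baseline-gap term and that moderation is tested on X×G×t. If the intervention effect is redefined as a post-baseline arm contrast, test X by that contrast instead. Leave the per-stage logistic interactions as they are.

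The cost is a few lines of SAP text and two more terms per moderator, with no new data and no design change. The real downside is lower power for X×G×t when a differential effect appears early and then wanes (20% against 38% in the example above), so the expected time course should guide the choice between the linear-time term and the post-baseline contrast.

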Study Protocol and Statistical Analysis Plan

Protocol Title: Depression Care to Improve Adherence to PMTCT Care Continuum and Pregnancy Outcomes

NCT03892915

Date: 4/16/19

Investigators:

1. [name], Makerere University, School of Public Health (Co-PI)
2. [name]; RAND Corporation (Co-PI)
3. [name]; Ministry of Health (Co-I)
4. [name], Makerere University, School of Medicine (Co-I)
5. [name]; Mulago Hospital (Co-I)
6. [name]; Mildmay Uganda (Co-I)

Brief outline of the rationale for the study

Depression is common among HIV+ pregnant women, in both prenatal and post natal phases and depression often impedes adherence to PMTCT care, parenting, and early child health development. Treating depression could mitigate these consequences and help ensure optimum pregnancy and maternal and child health outcomes. The proposed cluster randomized controlled trial will compare the effects of evidence-based depression care vs. usual care on adherence to each step of the PMTCT care continuum at 8 ANC clinics and with 400 HIV+ depressed pregnant women (50 per site). Four (4) clinics will implement usual care and 4 will implement usual care plus depression care [anti depressant therapy(ADT) and problem solving therapy (PST)]. Peer mothers will be trained to assist in depression screening and implement PST, while nurses will be trained to diagnose depression and provide ADT, under the supervision of psychiatric specialists. PST will be recommended for all women deemed eligible for treatment, while ADT will be recommended for only those with severe or refractory depression.

Primary aims of the study:

1. Integrate evidence-based PST and ADT into usual care, using the gold standard, stepped care approach.
2. Assess whether the integrated depression care model is superior to usual care on (1) adherence to each step of the PMTCT care continuum and maternal viral suppression (primary outcomes); (2) prevention of infant HIV infection, and maternal and child health outcomes (secondary outcomes), and 3) depression treatment uptake and depression alleviation (depression care processes).

Secondary aim;

Examine how (1) depression and (2) depression alleviation are associated with maternal viral load, adherence to each step of the PMTCT care continuum, and mother and child health outcomes; and identify potential mediators (e.g., HIV disclosure; stigma; problem solving skills) of these relationships.

Methods

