between fidelity measures (e.g. quality) and primary outcomes, as well as conduct mediation analysis including fidelity as a mediator, in the subgroup of patients enrolled in clinics receiving the intervention arm (depression care).

Secondary Aims 1 & 2: Explore relationship of depression and depression alleviation with primary and secondary outcomes. *Hypothesis: Depression will be associated with lower adherence to each step of the PMTCT care continuum, maternal viral suppression and maternal and child health, while depression alleviation will be associated with better adherence, viral suppression and health outcomes.* We will conduct (unadjusted) bivariate analysis to initially examine significant associations between baseline depression ($EPDS \geq 13$) and depression alleviation over time with the primary and secondary outcome measures. Next, longitudinal analysis will be conducted to incorporate repeated observations of individuals and to explore the relationship between change in depression and outcomes over time, and to test whether depression alleviation ($EPDS \leq 6$) is related to change in these outcomes. Models will control for observed individual characteristics and unobservables through a random effect term to incorporate characteristics that may affect both depression and the dependent variables. However, this model does not control for simultaneity (e.g., change in viral suppression leads to lower depression). With multiple time-points, instrumental variable approaches combined with fixed effects potentially can deal with this problem, using baseline depression to predict change in depression from time 2 to time 3, if baseline depression is strongly correlated with change in depression over time. The fixed effects model will indicate important time trends in depression and the primary and secondary outcomes.

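### Interactions with baseline characteristics are labelled tests of mediators, and the mediators named in the secondary aim have no mediation analysis

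*Combined protocol and SAP*

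**What the plan says.** The Secondary aim is to examine how depression, and its alleviation, relate to the mother's viral load, PMTCT adherence and the health of mother and child, and to "identify potential mediators (e.g., HIV disclosure; stigma; problem solving skills) of these relationships".

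In the Data analysis section, Primary Aim 1 adjusts the arm comparison for "patient characteristics such as age, CD4 and HIV disclosure status that may explain variance in observed differences". It will also "explore significant interactions between the covariates and study arm to assess which patient types are likely to be adherent". The repeated-measures model is then extended by a covariate vector X_i, which allows main effects and "interactions between these X_i and indicator of treatment group". The plan says this model will "test for significance of potential mediators: e.g., do effects of the depression care model vary by the patient's physical health at baseline".

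The plan then turns to how or why the intervention worked. There it will relate fidelity to the primary outcomes and "conduct mediation analysis including fidelity as a mediator, in the subgroup of patients enrolled in clinics receiving the intervention arm (depression care".

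The analysis for Secondary Aims 1 & 2 consists of bivariate associations, longitudinal random-effect models, and possibly instrumental variables combined with fixed effects. On confounding it says: "Models will control for observed individual characteristics and unobservables through a random effect term". Under Methods, the plan will enrol eligible women and "survey them at baseline, month 6, 12 and 18 following delivery".

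**The concern.** A mediator is something that the exposure changes and that in turn changes the outcome. A moderator is a characteristic across whose levels the effect differs. The test described under Primary Aim 1 is of the second kind but carries the name of the first. A woman's physical health at baseline is fixed before treatment starts. Neither the intervention nor later relief of depression can alter that value, so it cannot carry their effect.

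The section where the named mediators belong offers no method for them. Two things are at stake. A difference between baseline subgroups could be reported as a mediator. A real pathway, for example through problem solving skills or stigma, would not be tested at all.

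**Working it through.** The documents give no effect size, error rate or other figure for a mediation analysis, so there is no stated number to reproduce. The check is a comparison of the sections and a short piece of algebra.

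**1. Where each named mediator appears in the Data analysis section**

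| Item | Role in the Data analysis section |
|---|---|
| HIV disclosure | Adjustment covariate under Primary Aim 1; no mediator role |
| Stigma | Not mentioned |
| Problem solving skills | Not mentioned |
| Physical health at baseline | Example of a mediator, tested by interaction with arm |
| Fidelity | Mediator, intervention clinics only |

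None of the three mediators named in the Secondary aim has a mediator model or an indirect effect. The fidelity analysis does not fill the gap. It concerns a different variable, and within intervention clinics alone there is no contrast between arms.

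**2. What the interaction can show**

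Let G be study arm, X0 a baseline covariate, M a variable measured after randomisation and Y the outcome:

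- M = aG + e1
- Y = c'G + bM + e2

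Substituting the first line into the second gives Y = (c' + ab)G + (b·e1 + e2). The indirect effect is ab and the direct effect is c'. No G × X0 term appears, whatever the size of ab. Even if the whole effect runs through M (c' = 0), the coefficient on G × X0 is zero.

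Now take moderation with no mediation: b = 0 and Y = c'G + dX0 + fGX0 + e2. The indirect effect is a × 0 = 0, while the interaction coefficient is f, which can take any value.

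So the interaction can be zero under full mediation and non-zero under none. It becomes non-zero only if a, b or c' varies with X0. Suppose a = a0 + a1·X0 in the first model. The arm effect is then c' + a0·b + a1·b·X0, and the interaction is a1·b. Taken alone, that cannot be told apart from a direct effect that varies with X0. In neither case is X0 the mediator.

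The algebra is on the linear scale, which is how the plan writes its repeated-measures model. For the logistic models the decomposition is less tidy, but the reason is the same: X0 is set before G acts.

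**3. What the survey schedule allows**

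With surveys at baseline and at months 6, 12 and 18 after delivery, the following sequences put the mediator after the exposure and before the outcome:

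| Exposure | Mediator | Outcome |
|---|---|---|
| Baseline depression, or study arm | Month 6 | Month 12 or 18 |
| Alleviation by month 6 | Month 12 | Month 18 |

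Alleviation with a month-6 mediator would put both at the same survey and leave their order unknown. The first follow-up survey is 6 months after delivery, so PMTCT steps in pregnancy, at delivery or before that survey precede any follow-up measurement of a mediator.

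**The case against.** **A slip of one word.** The plan describes the same interactions correctly elsewhere, as a way to "explore significant interactions between the covariates and study arm to assess which patient types are likely to be adherent". The analysis is legitimate and only its label is wrong. This stands for the text under Primary Aim 1. Correcting the word, however, still leaves the Secondary aim without a method.

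**Two different questions.** A reader might infer that the Secondary aim fails because of the interaction test. The documents do not support that. The test sits under the comparison of arms, whereas the aim concerns how depression and its alleviation relate to the outcomes, and the plan never presents the interaction as the analysis for that aim. This objection stands in full: there is a mislabelled test in one place and a separate omission in another.

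**The plan does include mediation.** A reader might infer that it has none. It has one such analysis, for fidelity, and it places the question of how or why the intervention worked there. That also makes it conjecture that a subgroup difference would actually be published as a mechanism. Fidelity is nevertheless not one of the named mediators.

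**HIV disclosure has two roles.** It is both an adjustment covariate and a named mediator. Adjusting the arm comparison for a value measured after baseline could remove part of the effect, so a reader might infer that the primary analysis is biased. The documents do not show this. Disclosure is listed among patient characteristics and X_i has no time index, so baseline is the natural reading. Baseline adjustment does not conflict with a later mediator role. What remains is a request to state the timing.

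**Secondary and exploratory.** The aim is secondary and speaks of potential mediators. This limits the weight of the point but does not remove it.

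**Conclusion.** The point holds in two parts. First, the covariate-by-arm interactions test effect modification and by themselves carry no information on mediation. Second, the named mediators have no mediation analysis: the Secondary Aims text contains none, and the only one in the plan concerns fidelity within intervention clinics.

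The consequence is confined to one secondary aim. All three example mediators would go untested, and any moderators found would bear the wrong name. The primary comparison of arms is not affected. The change should be made, but the trial's main conclusion does not depend on it.

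The first part rests on the definition of a baseline value and on the algebra. The second rests on the text as it stands. Whether the gap can be filled depends on the mediators being measured at the follow-up surveys, which the documents do not state.

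**What to change.** 1. **Primary Aim 1.** For the interactions between X_i and arm, replace *potential mediators* with *potential effect modifiers*.

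2. **Secondary Aims 1 & 2.** Add an exploratory mediation analysis for HIV disclosure, stigma and problem solving skills that:
   - names the exposure and keeps the time order: baseline depression (or study arm), month-6 mediator, month-12 or month-18 outcome; and alleviation by month 6, month-12 mediator, month-18 outcome;
   - adjusts for the baseline value of the mediator, the baseline value of the outcome where one exists, and other baseline confounders of mediator and outcome;
   - accounts for clinic, for example by clinic indicators when the exposure is depression or alleviation. Arm is constant within a clinic, so for that exposure use the range of ICC values the plan already intends for its sensitivity analyses;
   - reports direct and indirect effects.

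3. **Primary models.** State that the HIV disclosure covariate is the baseline value. This is a clarification only.

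The cost is some rewording and a modest amount of extra analysis on surveys already scheduled. It assumes that the three mediators are asked about at follow-up. It cannot address PMTCT steps in pregnancy, at delivery or before the month-6 survey, and the plan should say so.

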The two arm cluster RCT will compare the effects of task-shifted, evidence-based depression care vs. usual care on adherence to each step of the PMTCT care cascade at 8 ANC clinics in Uganda. At 4 experimental sites, task-shifted, depression care will include (1) depression screening and psychoeducation, (2) depression diagnosis, and (3) provision of evidence-based problem solving therapy (PST), or antidepressant therapy (ADT) for those with severe and refractory depression (or who decline PST), to be implemented by trained peer mothers and midwife nurses. The 4 control sites will use usual care services for managing depression, which consist of the FSG program and referrals to a mental health specialist. At each site, 50 HIV+ newly pregnant women (total n=400) who screen positive for potential depression will be enrolled and followed until 18-months post-delivery to assess how depression and depression alleviation relate to primary (adherence to each component of the PMTCT care continuum, maternal virologic suppression) and secondary (infant HIV status; post-natal maternal and child health outcomes) outcomes, as well as processes of depression care (treatment uptake and depression alleviation among clinically depressed patients). The PST/ADT treatment will be provided only to study participants, not all depressed clients, because our focus is the effects of depression treatment on PMTCT adherence and pregnancy outcomes, not implementation research for scaling

up the model in ANC care (with HIV and non-HIV women), which is a much broader focus. A cost-effectiveness analysis will be used to compare the two study arms.

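### Alleviation is defined by EPDS of 6 or below alone in a cohort that includes women below 13 at baseline, so its association with outcomes can be biased in either direction

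*Combined protocol and SAP*

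**What the plan says.** **Entry.** The opening paragraph of Methods says that women "who screen positive for potential depression will be enrolled and followed until 18-months post-delivery". The next paragraph says that they are "screened for potential depression by trained peer mothers using the EPDS-2". A coordinator then confirms eligibility, but no full-EPDS threshold or diagnosis is given as an entry condition.

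**Exposures.** Secondary Aims 1 & 2 begins with an unadjusted step that looks for "significant associations between baseline depression ($EPDS \geq 13$) and depression alleviation over time with the primary and secondary outcome measures". The longitudinal analysis is then meant "to test whether depression alleviation ($EPDS \leq 6$) is related to change in these outcomes". No baseline score, size of fall or denominator is attached to alleviation.

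**A restriction elsewhere.** The Methods paragraph also lists "processes of depression care (treatment uptake and depression alleviation among clinically depressed patients" among what will be assessed. That limit belongs to alleviation as a care-process outcome. Earlier in the same sentence alleviation appears, without any limit, as something to be related to the primary and secondary outcomes.

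**The concern.** Baseline EPDS of 13 or more can serve as an exposure only if some enrolled women score below 13. For those women the alleviation rule has no sensible meaning, yet it still returns a value. A woman who moves from 8 to 6 is coded alleviated. A woman who stays at 8 is coded not alleviated. By the plan's own cut, neither had depression at baseline.

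Both sides of the contrast therefore blend women who were and were not depressed at baseline, usually in different proportions. The first analysis is unadjusted, and baseline EPDS is not named as a covariate in the later models. A positive finding could reflect who was depressed at the start, and a null finding could be a real association that has been watered down. The result could not be read with confidence either way.

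**Working it through.** **Inputs from the documents.** The sample is 8 clinics × 50 = 400. The cuts are 13 or more (baseline depression) and 6 or less (alleviation). The documents give no share of women at 13 or more, no alleviation rate and no adherence rate by depression status, so there is no stated figure to reproduce.

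**Assumptions.** A share f of women score 13 or more at baseline (0.5, 0.7 or 0.9). A score of 6 or less at follow-up is reached by a = 40% of these women and b = 70% of the others. Adherence is 60% in women depressed at baseline. All 400 contribute, and clustering is ignored.

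**Step 1: mixing.** The share of women below 13 at baseline is:
- in the alleviated group, wA = (1−f)b / [fa + (1−f)b];
- in the not-alleviated group, wB = (1−f)(1−b) / [f(1−a) + (1−f)(1−b)].

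| f | wA | wB | wA − wB |
|---|---|---|---|
| 0.5 | 0.35/0.55 = 64% | 0.15/0.45 = 33% | 0.303 |
| 0.7 | 0.21/0.49 = 43% | 0.09/0.51 = 18% | 0.252 |
| 0.9 | 0.07/0.43 = 16% | 0.03/0.57 = 5% | 0.110 |

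**Step 2: effect on the contrast**, in percentage points (alleviated minus not alleviated).

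| Scenario | Formula | f=0.5 | f=0.7 | f=0.9 | Baseline ≥13 only |
|---|---|---|---|---|---|
| A. Levels; no effect of recovery; others 10 points better | 10(wA−wB) | +3.0 | +2.5 | +1.1 | 0 |
| A. As above, others 20 points better | 20(wA−wB) | +6.1 | +5.0 | +2.2 | 0 |
| B. Change; recovery truly gains 10; others stable | 10(1−wA) | +3.6 | +5.7 | +8.4 | +10 |
| B. As above, true gain 15 | 15(1−wA) | +5.5 | +8.6 | +12.6 | +15 |
| C. Change; no effect; all women depressed at baseline improve by 10 | −10(wA−wB) | −3.0 | −2.5 | −1.1 | 0 |
| C. As above, all worsen by 10 | +10(wA−wB) | +3.0 | +2.5 | +1.1 | 0 |
| D. Levels; true effect 15; others at 75% | 15(1−wB) | +10.0 | +12.4 | +14.2 | +15 |

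Written out for A with f = 0.5 and a 10-point gap: alleviated (0.20×60 + 0.35×70)/0.55 = 66.4%; not alleviated (0.30×60 + 0.15×70)/0.45 = 63.3%; difference 3.0.

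Across scenario A, a two-sided 5% test on 400 women gives a significant favourable result with probability 4% (f = 0.9, gap 10) to 26% (f = 0.5, gap 20), against a nominal 2.5%.

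B and C can act together. With a true gain g and a common change r in women depressed at baseline, the observed difference is g(1−wA) − r(wA−wB). At f = 0.5 with g = r = 10 this is 3.6 − 3.0 = 0.6. The sign reverses once r exceeds 10 × 0.364/0.303 = 12 points.

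**Step 3: other assumptions.** Take no effect of recovery and adherence of 60% and 80% in women at or above and below 13.
- f = 0.6, a = 30%, b = 60%: 0.300/0.42 = 71.4% against 0.380/0.58 = 65.5%, a gap of 5.9 points. Of the alleviated, 0.24/0.42 = 57% were below 13 at baseline.
- f = 0.8, a = 40%, b = 50%: 0.272/0.42 = 64.8% against 0.368/0.58 = 63.4%, a gap of 1.3 points before rounding. The share is 0.10/0.42 = 24%.

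If a = b, then wA = wB. The artefacts in A and C vanish, but the dilution in B and D remains.

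**The case against.** **Alleviation presupposes depression.** In ordinary usage it does. Methods attaches the term to clinically depressed patients once, and the rationale speaks of "400 HIV+ depressed pregnant women (50 per site". A sensible analyst might apply the restriction unprompted. It is therefore fair to say that the plan permits this coding and does not expressly prescribe it. But a variable is coded from its stated rule, that rule is a score alone, and using baseline depression as an exposure shows that the cohort is not uniformly depressed.

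**The later models help.** The section also studies change in depression, adjusts for individual characteristics, adds a random effect, and raises instrumental variables with fixed effects. It openly admits simultaneity. Part of this stands: fixed effects would remove stable differences between women. But they are offered only as a possibility, and a move from 8 to 6 would still count as alleviation. A random effect is normally assumed independent of the covariates, so it does not remove confounding by baseline depression. Nothing protects the first, unadjusted step.

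**The direction is not fixed.** A reader might infer that the mixing tilts the result towards the trial's hypothesis. The documents do not support that. It follows for unadjusted levels when recovery has no effect and women below 13 do better (scenario A). The quoted test concerns change in outcomes, where B and C show dilution or artefacts of either sign, and D shows dilution of levels when a true effect exists.

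**These women were not shown to be never depressed.** This is correct. All screened positive, and a score below 13 at one visit says nothing about earlier or later depression. Restricting every analysis to baseline EPDS of 13 or more would also lose women who become depressed after delivery and then recover. The fix has to allow for them.

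**Conclusion.** The concern holds as a defect of definition. Secondary Aims 1 & 2 applies a rule based on one score to a cohort that must include women below the plan's own cut, and does not carry over the restriction that Methods states for the process outcome. Taken literally, the rule misclassifies some women in both groups.

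The size depends on rates that the documents do not give. Under the main assumptions, 16% to 64% of women coded alleviated would have been below 13 at baseline, and the distortion runs from about 1 to 6 points in the scenarios with no true effect. It is small when nearly all enrolled women score 13 or more. That the association can be biased is secure; a particular direction is not.

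Nor should a reader infer that the trial's main result is at risk. The aim is exploratory, and the arm comparison under Primary Aim 1 does not use this definition. The point is worth correcting before analysis but does not threaten the trial.

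**What to change.** In Secondary Aims 1 & 2:
- Define alleviation as baseline EPDS of 13 or more and follow-up EPDS of 6 or less.
- Run the main alleviation analyses, including the bivariate step, in women with baseline EPDS of 13 or more, comparing those who reach 6 or less with those who do not.
- Adjust the models for the baseline EPDS score, since women nearer 13 are likely to reach 6 more easily.
- Report women below 13 separately as not depressed at baseline.
- Add a sensitivity analysis that counts recovery from any earlier study visit with EPDS of 13 or more, to capture depression that starts after baseline.
- Reconcile this wording with the clinically depressed population named in Methods, and say whether the two are the same.

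The change is to wording only and uses data already planned. The cost is precision: the main analyses use 400f women, that is 200, 280 or 360 for f = 0.5, 0.7 or 0.9. With a similar split and variance, intervals widen by about 1/√f, or 1.41, 1.20 and 1.05 times.
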